5.6.6 Other Safety Analyses

5.6.6.1 Adverse Events of Special Interest

The incidence of treatment-emergent adverse events and treatment-related, treatment-emergent adverse events of special interest will be summarized by treatment group.

Adverse events of special interest include:

- Recurrence of thrombocytopenia (platelet count of $<10 \times 10^9/L$ and $10 \times 10^9/L$ less than baseline count within 30 days of discontinuation)
- Thromboembolic events
- Bleeding events (WHO Grade 2 to 4)

Recurrence of thrombocytopenia events include the adverse events with MedDRA preferred term belonging to 2nd level Standardized MedDRA Query (SMQ) 'Haematopoietic thrombocytopenia' and with 'Event of Special Interest per Protocol Definition' checked as 'Yes' on the AE CRF page.

Thromboembolic events include the adverse events with MedDRA preferred term belonging to SMQ 'Embolism and thrombotic events'.

Bleeding events (WHO Grade 2 to 4) include the adverse events with MedDRA preferred term belonging to 2nd level SMQ 'Haemorrhage terms (excl laboratory terms)' and with WHO Bleeding Scale score 2 to 4.

Additionally the incidence of treatment-emergent adverse events and treatment-related, treatment-emergent adverse events for thromboembolic events will be summarized by treatment group and by HCC status.

5.6.6.2 Doppler Sonography

The results from Doppler Sonography will be presented in the listings only.

5.6.6.3 Platelet Function Test

For each parameter of platelet function assessed via flow cytometric markers, the actual value and changes from baseline will be summarized by visit and treatment group using descriptive

statistics. Analysis of changes from baseline will be based on the number of subjects with both nonmissing baseline and relevant postbaseline results.

Only listings will be provided for platelet function assessed using platelet aggregometry.

5.7 OTHER ANALYSES

5.7.1 Health Outcome Economics Analyses

Health outcome economics data will be listed in the subject data listings only.

5.8 EXPLORATORY ANALYSES

Exploratory analyses may be conducted as appropriate. Any exploratory analyses that are performed will be appropriately titled/labeled as exploratory and will be clearly distinguished from planned analyses when results are reported in the Clinical Study Report.

5.9 EXTENSION PHASE ANALYSES

Not applicable.

6 INTERIM ANALYSES

No interim efficacy analysis is planned for this study, and therefore no adjustment of the *P*-value for the final efficacy analysis is needed. However, to protect subjects' safety, an independent DSMB will be established to monitor the ongoing safety data in unblinded manner. To maintain the blinding of DSMB members on the efficacy data, no platelet transfusion data, by-subject listing on platelet count, and by-visit summary on platelet count and change from baseline in platelet count will be sent to DSMB. The only information DSMB will receive on platelet count is the percentage of subjects with extreme values (eg, exceeds $200 \times 10^9/L$) for safety reason. The DSMB safety interim analysis will be performed by an independent statistician and governed by an external DSMB. To maintain the blinding and integrity of the study, procedures will be implemented to ensure the DSMB and independent statistician have sole access to unblinded interim safety data.

Full details of the DSMB procedures including primary responsibilities of the DSMB, its relationship with other study components, its membership, and the purpose and timings of its meetings will be documented in a DSMB charter. These details will also include procedures to ensure confidentiality and proper communication, the guidelines to be implemented by the DSMB, and an outline of the content of the closed reports (unblinded) and open reports (blinded) that will be provided to the DSMB.

7 CHANGES IN THE PLANNED ANALYSES

SAP version (Final 3.0) is updated based on Protocol Amendment 04 with the following changes:

- Sections 3.1.2, 3.1.3, 5.1.2, 5.1.3, 5.3.3.1, 5.4.2, 5.4.2.3, 5.4.3 and 5.4.3.5: Efficacy endpoint "Proportion of subjects with a WHO bleeding score ≥ 2 after randomization and

up to 7 days following an elective procedure” is moved from secondary to exploratory endpoint to match the protocol amendment 4. These sections have been updated to reflect this change.

- Section 4: Sample size is reduced from 300 to 200. This section has been updated to match the protocol amendment 4.
- Section 5.4.2.2: Calculation of 95% CI for change from baseline in platelet count on Procedure Day for each treatment group within each baseline platelet count cohort has been removed to ensure consistency with the study objectives.
- Section 5.7.1: This section is updated to reflect that only listings will be provided for the Health Economics Assessment.
- Section 5.2.1: Per-Protocol exclusion criteria are finalized.

SAP version (Final 2.0) was updated based on Protocol Amendment 02 with the following changes:

- Section 3.2 table 1, and sections 5.2.4, 5.3.2, 5.3.4, 5.4.1, 5.4.1.2 and 5.4.2.1: Categorization of risk of bleeding is updated to match protocol amendment 02
- Section 5.6.6.3: Listing of platelet function test assessed using platelet aggregometry has been added.
- Section 13.1: "Fasting Glucose value" has been added to the criteria for determining grade 3 and 4 in the lab grading table.

SAP version (Final 2.0) was also updated from version Final 1.0 to ensure consistency with the eCRF/protocol as follows:

- Section 5.6.5: ECG interpretation category is updated.
- Section 5.2.4: Baseline summaries of creatinine clearance and disease etiology, and subgroup analysis by disease etiology have been added.

8 DEFINITIONS AND CONVENTIONS FOR DATA HANDLING

8.1 VISIT WINDOW

Study Day 1 is defined as the date of the first dose of study drug. The analysis visits defined below will be used in the by-visit summaries:

Visit	Target Visit Date	Visit Window	Analysis Visit
Visit 2 (Baseline)	Study Day 1	Less or equal to Study Day 1	Last visit on or before Study Day 1
Visit 3	Study Day 4	Study Day 2 to 7	Closest visit to Study Day 4
Visit 4	Study Day	Subjects with procedure:	Subjects with platelet

Visit	Target Visit Date	Visit Window	Analysis Visit
(Procedure Day)	10 to 13	Study Day 8 to actual procedure day Subjects without procedure: Study Day 8 to 13	transfusion: last visit before transfusion Subjects with procedure but without transfusion: last visit before procedure Subjects without platelet transfusion or procedure: closest visit to Study Day 10
Visit 5	7 Days post procedure	Subjects with procedure: 1 to 10 days post actual procedure day Subjects without procedure: Study Day 14 to 20	Subjects with procedure: visit closest to 7 days post actual procedure day Subjects without procedure: closest visit to Study Day 17
Visit 6	Study Day 35	Subjects with procedure: Greater or equal to actual procedure day +11 days Subject without procedure: Greater or equal to Study Day 21	Closest visit to Study Day 35

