**Table 5 Schedule of Procedures/Assessments in Study E5501-G000-310**

pharmacokinetics; TPO = thrombopoietin; WHO = World Health Organization

- a: Subjects will undergo their elective procedure within 5 to 8 days of their last dose of study drug (ie, Study Day 10 to 13), and after completing the Procedure Day assessments.
- b: Visit 4 (Procedure Day) assessments will also occur when any subject has been withdrawn or discontinued early from the study for any reason.
- c: Visit 6 (Day 35) assessments will also occur when any subject has been withdrawn or discontinued early from the study for any reason.
- d: BCLC grade is only for subjects with hepatocellular carcinoma.
- e: Comprehensive physical examination at Screening and targeted physical examination at all subsequent visits.
- f: Height will be recorded at Screening (Visit 1) only.
- g: Hematology must be taken prior to any platelet transfusion
- h: Independent platelet counts performed by a local laboratory at Screening and Baseline must be at least 1 day apart with neither platelet count  $>60 \times 10^9/L$ . The mean of these 2 platelet counts (mean baseline platelet count) must be  $<50 \times 10^9/L$  (as per Inclusion Criterion #2), to be eligible to participate in the study.
- i: Complete urinalysis will be performed at Screening and dipstick analysis at all subsequent visits. If urine dipstick is abnormal, a complete urinalysis will be required. After the Screening measurement, fractionation will only be analyzed by the central laboratory in the event CPK level is abnormal.
- j: For females of childbearing potential or who have been amenorrheic for less than 12 months. Serum beta-human chorionic gonadotropin pregnancy testing will be performed at Screening (Visit 1). Urine pregnancy testing will be performed at Visits 2, 4, and 6.
- k: Portal vein flow velocity will be assessed at this visit. Subjects will be required to have a main portal vein blood flow velocity rate of  $\geq 10$  cm/second at Screening to be eligible for the study.  
Three main portal vein blood flow velocity measurements, lasting no less than 4 seconds, will be recorded, and the mean of the 3 values recorded as the final reading.  
The Doppler sonography and flow rate assessment can be completed at any time during the Screening Period with results available prior to randomization.

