5.4.2 Secondary Efficacy Analyses

There are 2 secondary efficacy endpoints in this study:

- Proportion of responders, defined as subjects who achieve target platelet counts of $\geq 50 \times 10^9/L$ on Procedure Day (prior to receiving a platelet transfusion or undergoing the elective procedure)
- Change from baseline in platelet count on Procedure Day (prior to receiving a platelet transfusion or undergoing the elective procedure)

The analysis of the secondary efficacy variables, as defined above, will proceed following a sequential gatekeeping testing procedure to control the family-wise Type I error rate at a significance level of $\alpha=0.05$.

5.4.2.1 Proportion of subjects achieved platelet counts of $\geq 50 \times 10^9/L$ on the Procedure Day

The proportion of subjects who achieve platelet counts of $\geq 50 \times 10^9/L$ on the Procedure Day will be analyzed first.

The proportion of subjects with platelet counts of $\geq 50 \times 10^9/L$ on the Procedure Day will be tested between the individual avatrombopag treatment group (40 or 60mg) and matching placebo separately within each baseline platelet count cohort ($< 40 \times 10^9/L$ or from 40 to $< 50 \times 10^9/L$), each at a significance level of $\alpha=0.05$ using the generalized CMH test adjusting for the risk of bleeding associated with the elective procedure (low, moderate, or high based on Amendment 02 categorization).

The 95% CI for the proportion of subjects with platelet counts of $\geq 50 \times 10^9/L$ on the Procedure Day will be calculated for each treatment group within each baseline platelet count cohort. In addition, the 95% CI for the difference between avatrombopag and placebo will also be provided within each baseline platelet count cohort using normal approximation method.

Subjects with missing platelet count on Procedure Day will be considered as not achieving the platelet count of $\geq 50 \times 10^9/L$ for this analysis.

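### For subjects given platelets after the procedure, SAP 8.1 caps the Procedure Day count by calendar day only, so a same-day post-procedure count can be selected

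*SAP*

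**What the plan says.** SAP 5.1.2 and 5.4.2, like protocol 9.7.1.1 and 9.7.1.6, define both secondary endpoints (reaching 50 × 10⁹/L, and change from baseline) by the platelet count "on Procedure Day (prior to receiving a platelet transfusion or undergoing the elective procedure".

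SAP 8.1 gives the Visit 4 row two columns that work together:

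- Window, for every subject with a procedure: "Study Day 8 to actual procedure day".
- Analysis visit within that window, first for subjects with platelet transfusion and then for the others who had a procedure: "transfusion: last visit before transfusion Subjects with procedure but without transfusion: last visit before procedure".

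The Visit 5 window starts the day after the procedure: "1 to 10 days post actual procedure day". The table is introduced with this statement of scope: "The analysis visits defined below will be used in the by-visit summaries".

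On timing, protocol 9.1.2.3 and Table 5 footnote a place all Visit 4 assessments ahead of the procedure. Footnote g to the haematology row adds: "Hematology must be taken prior to any platelet transfusion".

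**The concern.** The endpoint definition sets two limits on the count: before transfusion and before the procedure. The selection rule carries both over only in part. A subject without transfusion is held to a pre-procedure count. A subject with transfusion is held to a pre-transfusion count, and the procedure enters only through the last day of the window. That day includes the hours after the procedure.

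The case that slips through is a subject who goes into the procedure without platelets, has a further local count later the same day, and then receives platelets that day or on a later day. The further count is in the window and precedes the transfusion, so the rule takes it in place of the pre-procedure count. The value then describes the subject after the procedure, possibly after a bleed, and no longer answers the question that the endpoint asks.

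The Visit 4 rows of the exploratory analyses in SAP 5.4.3.1 and 5.4.3.2 use this value directly. The two tested secondary endpoints would use it too if the table also supplies their Procedure Day count; the SAP gives no other derivation.

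**Working it through.** The plan states no figure on this point. Its one power figure (above 90% per cohort, SAP 4) reproduces at 0.926 by exact enumeration of Fisher's test with 67 versus 33 subjects and 53% versus 18% response. It does not enter the argument; only the arm sizes are used below.

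**Applying the rule.** Six hypothetical timelines were run through the window column and then the analysis-visit column. Times are study days with the decimal as the fraction of the day. The procedure is at 10.5 and the scheduled Visit 4 count at 10.3. The last column adds a limit at the time of the procedure.

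| Timeline | Further counts | Transfusion | SAP 8.1 selects | With limit at procedure |
|---|---|---|---|---|
| 1. Transfused before procedure | none | 10.4 | 10.3 | 10.3 |
| 2. Transfused two days after | 11.4, 12.4 | 12.5 | 10.3 | 10.3 |
| 3. Visit 5 count, then transfused | 17.3 | 18.0 | 10.3 | 10.3 |
| 4. Same-day count, same-day transfusion | 10.7 | 10.8 | **10.7** | 10.3 |
| 5. Same-day count, next-day transfusion | 10.7 | 11.2 | **10.7** | 10.3 |
| 6. Transfused before Day 8 | none | 6.5 | none | none |

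Timelines 2 and 3 are safe because the window shuts out counts from later days. Timelines 4 and 5 fail: the selected count at 10.7 precedes the transfusion but follows the procedure at 10.5. The added limit repairs those two and changes nothing else. Timeline 6 has no eligible count under either rule.

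**Size per subject.** SAP 4 plans 67 avatrombopag and 33 placebo subjects per cohort. One responder who flips changes the arm's rate by:

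- avatrombopag: 1/67 = 1.5 points
- placebo: 1/33 = 3.0 points

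**How many subjects.** The documents give no rate. Purely as an assumption, let 1% to 5% of subjects have both a post-procedure platelet transfusion and a same-day post-procedure count before it:

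- avatrombopag: 0.01 × 67 = 0.7 to 0.05 × 67 = 3.4
- placebo: 0.01 × 33 = 0.3 to 0.05 × 33 = 1.7

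These are subjects whose value is replaced. A responder flips only if the first count was at least 50 × 10⁹/L and the second was below it, so flips are no more frequent and probably rarer. The Amendment 04 rationale records fewer bleeding events than expected, which argues against the upper end.

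**The case against.** **The endpoint definition governs.** It already excludes a post-procedure count, the visit table is introduced for by-visit summaries, and SAP 9 leaves derivation rules to separate documents. It is therefore an inference that the table supplies the secondary endpoints. That stands. But the SAP offers no other rule for the Procedure Day value, and the Visit 4 exploratory rows use the table in any case.

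**Visit 4 is a pre-procedure visit.** The protocol schedules no post-procedure sample on that day, so the failure needs an unscheduled local count that is entered as an analysis record. This also stands, and it is why the case is narrow. The separate wording for untransfused subjects shows that the authors did not rely on the schedule alone.

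Four stronger readings are tempting, and the documents do not support them.

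- A reader might infer that transfused subjects have no limit at the procedure at all. The window column ends at the procedure day for them too, and later counts belong to Visit 5.
- A reader might infer that every transfused subject is exposed. Those transfused only before the procedure get a correct value.
- A reader might take footnote g as ordering a fresh sample before each rescue transfusion, so that the protocol itself creates the second count. The footnote belongs to the scheduled haematology row and is more naturally read as timing that sample.
- A reader might infer a bias against avatrombopag, because more of its subjects should reach the procedure without platelets. That is plausible reasoning from the planned response rates, but the documents give neither a rate nor a direction for the affected cases.

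**Conclusion.** The rule is wrong as written, in a narrow case. For a subject given platelets after the procedure, SAP 8.1 can select an unscheduled same-day count taken after the procedure, which the definition of both secondary endpoints rules out. This is more than missing detail: followed literally, the stated rule returns the wrong value.

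The effect is small and its total cannot be computed from the documents. The conclusion rests on two conditions: that such a same-day count is drawn and enters the analysis data, and, for the secondary endpoints, that the SAP 8.1 table is the source of their Procedure Day value. Nothing here suggests that the outcome of either secondary test would change.

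**What to change.** In SAP 8.1, Visit 4, replace the first two analysis-visit rules with one: for subjects with a procedure, use the last count within the existing window that precedes both the platelet transfusion, if there is one, and the procedure. Keep the present rule for a subject who is transfused but has no procedure. State in the same place that the table also supplies the Procedure Day value for the secondary endpoints, if that is intended.

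The clock time of each local platelet sample is already collected (protocol 9.5.1.5, Laboratory Measurements), as are transfusion start and stop times (protocol 9.5.1.3). The documents do not show that the procedure's start time is recorded. If it is not, use the scheduled Visit 4 sample, which protocol 9.1.2.3 requires before the procedure, in preference to any unscheduled count that day.

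The rule should not be tied to the first platelet transfusion after randomisation. A subject transfused before Day 8 and again on Procedure Day would then have no eligible count in the window, would count as a non-responder under SAP 5.4.2.1, and would lose a Visit 4 count that exists.

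The cost is one line of SAP text and the matching program change, made before unblinding. No data collection or clinical conduct changes.

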Within the **lower** baseline platelet count cohort ($<40 \times 10^9/L$) and each stratum, subjects will be randomized in a 2:1 ratio to receive avatrombopag or matching placebo as follows:

- 60 mg avatrombopag on Days 1 to 5 (Group A)
- Matching placebo on Days 1 to 5 (Group B)

Within the **higher** baseline platelet count cohort (from 40 to $<50 \times 10^9/L$) and each stratum, subjects will be randomized in a 2:1 ratio to receive avatrombopag or matching placebo as follows:

- 40 mg avatrombopag on Days 1 to 5 (Group C)
- Matching placebo on Days 1 to 5 (Group D)

Platelet counts must be measured on 2 separate occasions, during the Screening Period and at Baseline, and must be performed at least one day apart with neither platelet count $>60 \times 10^9/L$. The average of these 2 platelet counts will be used for entry criteria (the mean baseline platelet count of $<50 \times 10^9/L$). The elective surgical or diagnostic procedure is scheduled to be performed within 10 to 13 days of first dose of study drug.

This study will consist of 3 phases: Prerandomization, Randomization, and Follow-up Phases.

The Prerandomization Phase consists of a Screening Period (Visit 1) that will take place from Day -14 through Day -1. During this period, the type and schedule of the elective procedure will be confirmed.

The Randomization Phase includes the Baseline Period, Treatment Period, and Procedure Day. During the Baseline Period (Visit 2), subjects who have met all entry criteria, provided signed informed consent, and been randomized will be instructed to take study drug during the Treatment Period on Days 1 to 5. During the Treatment Period, subjects will come in for PK samplings on Day 4 (Visit 3). The elective procedure will be performed 5 to 8 days after last dose of study drug (Study Day 10 to 13) after all assessments on Visit 4 (Procedure Day) have been performed. The elective procedure for those subjects whose preprocedural platelet count is $>200 \times 10^9/L$ on Visit 4 may be delayed at the discretion of the investigator until platelet counts are below $200 \times 10^9/L$. All subjects whose platelet count exceeds $200 \times 10^9/L$ will be required to have a Doppler assessment at Visit 5.

The Follow-up Phase encompasses 2 visits: 7 days post Procedure Day (Visit 5) and 30 days after receiving the last dose of study drug (Visit 6).

An overview of the study design is presented in [Figure 1](#)

[figure not shown]

Figure 1 Study Design

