5.4.3.1 Platelet count and change from baseline in platelet count at each visit

Platelet count and change from baseline in platelet count will be compared between individual avatrombopag (40 or 60mg) and matching placebo separately within each baseline platelet count cohort at a significance level of $\alpha=0.05$, using the Wilcoxon rank sum test based on observed data. Missing values will not be imputed.

5.4.3.2 Proportion of responders defined as subjects who achieve platelet counts of $\geq 50 \times 10^9/L$, $\geq 75 \times 10^9/L$, or $\geq 200 \times 10^9/L$ at each visit

The number and percentage of responders will be summarized by treatment group within each baseline platelet count cohort at each visit. Missing values will not be imputed.

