5.6.3 Laboratory Values

Laboratory results will be summarized using Système International (SI) units, as appropriate. With the exception of urinalysis, platelet function tests and platelet count (which is considered as an efficacy parameter), for all quantitative parameters listed in [protocol Section 9.5.1.5 Safety Assessments \(Laboratory Measurements\)](#), the actual value and the change from baseline will be summarized by visit and treatment group using descriptive statistics. Analysis of changes from baseline will be based on the number of subjects with both nonmissing baseline and relevant postbaseline results.

Laboratory test results will be assigned a low/normal/high (LNH) classification according to whether the value is below (L), within (N), or above (H) the laboratory parameter's reference range. Shifts from baseline (LNH) to Procedure Day and to the end of the Follow-up Phase will be presented for each laboratory parameter. Similar shift tables from baseline (LNH) to the highest/lowest postbaseline LNH classification will also be provided. A subject will be counted once in highest LNH classification and once in the lowest LNH classification.

The Sponsor's Grading for Laboratory Values (see [Appendix 1](#)) presents the criteria that will be used to identify subjects with treatment-emergent markedly abnormal laboratory values (TEMAV). Except for phosphate, a TEMAV is defined as a postbaseline value with an increase from baseline to a grade of 2 or higher. For phosphate, a TEMAV was defined as a postbaseline value with an increase from baseline to a grade of 3 or higher. When displaying the incidence of TEMAVs, each subject will be counted once in the laboratory parameter high and in the laboratory parameter low categories, as applicable.

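### Could a platelet count above 200 × 10⁹/L drop out of the final tables when the procedure is delayed and the count repeated?

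*SAP*

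**What the plan says.** SAP 8.1 gives subjects with a procedure a Visit 4 window of "Study Day 8 to actual procedure day". Within it, one record is used: "Subjects with procedure but without transfusion: last visit before procedure". For transfused subjects it is the final visit preceding the transfusion. These analysis visits feed the by-visit summaries.

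SAP 3.2, like Protocol 9.1.2.3, says that for a pre-procedure count above 200 × 10⁹/L at Visit 4 the procedure "may be delayed at the discretion of the investigator until platelet counts are below" that level. A Doppler assessment at Visit 5 is then required.

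The one final summary with a cut at 200 is SAP 5.4.3.2: "The number and percentage of responders will be summarized by treatment group within each baseline platelet count cohort at each visit". SAP 5.6.3 leaves platelets out of the laboratory value and change summaries, giving as its reason "platelet count (which is considered as an efficacy parameter"). Its next paragraph, on shift tables, repeats no such exception: "Similar shift tables from baseline (LNH) to the highest/lowest postbaseline LNH classification will also be provided". SAP 5.6.6.2 adds: "The results from Doppler Sonography will be presented in the listings only". SAP 6 gives the DSMB the percentage of subjects with extreme counts, as interim information only.

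**The concern.** The Visit 4 window lengthens with any delay and the latest record wins. A subject postponed because of a high count is, by the terms of the postponement, likely to have a lower count at the end of the window. Read literally, the rule can therefore drop from the row for 200 or more the subjects whose high count changed their management.

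Protocol 7.2.1 and 9.4.4 explain the doses by the aim of keeping the share above 200 under 2%, against a background of portal vein thrombosis with a similar drug. If the final row understated that share, a reader might take the aim as met when it was not. With so few subjects expected above 200, losing one or two would show in the percentage.

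**Working it through.** **1. Tracing one subject.** The values are illustrative: 230 on Day 10, procedure postponed for that reason, repeat 180, procedure on Day 14, no transfusion.

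- Visit 3 window, Days 2 to 7: the 230 is too late.
- Visit 4 window, Day 8 to Day 14: if the repeat is a visit, it is the later record and Visit 4 is 180. If it is not, Visit 4 is 230 and the subject is counted.
- Visit 5 window, 1 to 10 days after the procedure, so Days 15 to 24: the 230 is too early.
- Visit 6 window, from the procedure day plus 11, so from Day 25: the 230 is too early.

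Under the first reading no analysis visit uses the 230. Under the second nothing is lost. SAP 8.1 does not choose between them. SAP 9 and SAP 11 refer to separate documents that may do so.

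**2. Other outputs that could show the 230.**

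- Shift to the highest post-baseline class (SAP 5.6.3): if platelets are included, a count above the laboratory's upper limit appears as high. A count between 200 and that limit does not. The limit is not in the documents.
- Adverse event tables: Protocol 9.5.1.5 makes a laboratory abnormality an adverse event if it leads to intervention, or in the investigator's judgement. Nothing makes this automatic above 200.
- Markedly abnormal values (SAP 13.1): platelets are graded for low counts only.
- Doppler listing: the Visit 5 examination required for counts above 200 identifies such subjects indirectly.

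So no described final table is certain to show the excess at a cut of 200, though some may.

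**3. Size.** The plan's one reproducible figure is its power. With 67 against 33 subjects, 53% against 18%, and Fisher's exact test at two-sided 0.05, exact enumeration gives 92.6%, in line with the stated figure of over 90%. It concerns the primary endpoint and is not touched here. The 2% projection comes from modelling outside the documents and cannot be reproduced, so it is used as an assumption.

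Inputs: n = 133 avatrombopag subjects, 67 per cohort (SAP 4); p = 0.02 (the ceiling of the projection); s = share of those above 200 who are delayed for it and have a qualifying repeat below 200. The documents do not give s, so a range is shown.

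Expected above 200: 133 × 0.02 = 2.66. Expected loss from the row: n × p × s. Chance of losing at least one: 1 − (1 − p × s)^133.

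| s | Expected loss | Chance of at least one |
|---|---|---|
| 0% | 0 | 0% |
| 10% | 0.27 | 23% |
| 25% | 0.67 | 49% |
| 50% | 1.33 | 74% |
| 100% | 2.66 | 93% |

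One subject is 1/133 = 0.75 percentage points overall, or 1/67 = 1.49 in a cohort row. As an illustration, 4/133 = 3.0% (exact 95% CI 0.8 to 7.5) would become 2/133 = 1.5% (0.2 to 5.3) if two subjects were lost. The point estimate crosses 2%, but both intervals contain 2%.

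**4. Direction.** Protocol 7.1.2.3 reports the highest Phase 2 responses between Days 10 and 14, so a procedure delayed for an unrelated reason could move a subject upward across 200. The losses are cancelled if a share u = p × s / (1 − p) of the other subjects does so: 0.20%, 0.51% and 1.02% at s = 10%, 25% and 50%. The documents do not say how often such delays occur, so the net direction is unknown.

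**The case for a change.** The best argument for a change starts from the wording. A rule that picks the latest visit has something to choose only if the window can hold more than one, and Protocol Table 5 schedules just one there. That suggests repeats were meant to qualify. The doses were chosen, and the DSMB watches, with the 200 threshold in mind, yet the final analysis promises no any-time counterpart. A sentence and one descriptive table would cost almost nothing. SAP 5.8 ("Exploratory analyses may be conducted as appropriate") permits such a table but does not commit to it.

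Part of this stands. SAP 8.1 is silent on unscheduled counts, and the literal reading does produce the loss traced above. It does not establish an error, for three reasons.

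- The endpoint is the proportion at each visit, in Protocol 9.7.1.1 and SAP 5.1.3 alike. The row is being measured against a quantity it was not defined to estimate. A pre-procedure record at Visit 4 is what the secondary endpoints require.
- The protocol does not state whether its 2% refers to any day or a given day. The any-time reading is an inference from its wording.
- Advance naming guards against selective reporting, but counting subjects with any value above a threshold already fixed in the protocol leaves little to select. It involves no test and no alpha.

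**Conclusion.** No change is needed. This is an unstated data-handling convention that programmers settle in the specifications, together with a possible extra table that the plan already permits. Local platelet counts are entered in the CRF with their sampling times (Protocol 9.5.1.5, below Table 4), so any recorded count above 200 can be retrieved whichever reading of a visit is adopted.

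The effect is confined to one exploratory row. It is zero if repeats are not visits. Otherwise it is 0.27 to 1.33 expected subjects of 133, assuming 2% exceed 200 and 10% to 50% of those are delayed and rechecked below it. The ceiling is 2.66 at that 2%, and would be higher in proportion if the true rate were higher. Subjects above 200 who proceed on schedule stay in the row. The primary endpoint, both secondary endpoints and the thromboembolic event tables do not depend on it, and the 2% is a dose-selection projection on which no decision rests. An analyst who wants the any-time share can tabulate it without amending the SAP.
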